Data from source documents will be entered and validated in a REDCap database for which special privacy and security measures are in place. All data entered into REDCap will be de-identified and collected data will only be viewed by study team members granted specific rights. REDCap has the capacity to store 'live' data for multiple, ongoing study databases simultaneously where each individual study database has the option of supporting multiple centers. The REDCap database will be provided by the CHILD-BRIGHT Data Coordinating Centre (DCC) which is managed by the Women & Children's Health Research Institute at the University of Alberta. The database itself is housed on secure servers hosted in a secure data Centre in the basement of the University of Alberta Hospital behind the MEDIT firewall. The REDCap database will be annulled and the electronic data deleted 5 years after the study has been completed.

REFERENCES

1. Perquin CW, Hazebroek-Kampschreur AAJM, Hunfeld JAM, et al. Pain in children and adolescents: a common experience. *Pain*. 2000;87(1):51-58. doi:10.1016/S0304-3959(00)00269-4.
7. Hunt AM. A Survey of Signs, Symptoms and Symptom Control in 30 Terminally Ill Children. *Dev Med Child Neurol*. 1990;32(4):341-346. doi:10.1111/j.1469-8749.1990.tb16946.x.

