- Even multiple attempts by diverse care teams were unable to resolve PIUO. Children continued to experience PIUO despite assessments by 6 to 14 different clinical teams and primary care providers prior to enrolment.
- Pediatric symptom management experts could not agree on treatment strategies. For example, there was a complete lack of consensus about optimal pharmacotherapy for PIUO.
- For pilot study participants, PIUO was resolved for 63% in ~13 weeks (median). These children had shown signs of PIUO for 1-2 years prior to study entry, but our stepwise evaluation and treatment sequence (led by an RN and MD) resolved it for nearly two-thirds of the children in 1-25 weeks.

If our current study confirms the outcomes from our pilot study - that the PIUO Pathway can be useful in addressing the vexing problem of PIUO in children with SNI, the results will create the first-ever systemized practice guideline to treating pain in this challenging and vulnerable population based on a solid evidence base. Ultimately, such guidelines will streamline pain manage-

ment for this population and improve the children and their families' well-being. The results will inform families, front-line clinicians, and researchers about better ways to address one of the most troubling symptoms occurring in children with complex, incurable conditions.

STUDY DESIGN

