at any time during the study (standard working hours) in between the scheduled bi-weekly phone call. The Pain Survey tool measures pain and irritability persistence and distress level through a composite score of two questions asking parents to report on their child's experience and behavior within the last two weeks. The tool is taken from the Washington Group Extended Question Set on Functioning (WGES- F) developed by a United Nations commission on disability statistics and is intended to capture a measure of physical impairment along with questions on pain, fatigue and depression. The extended set of questions has been adopted by the United Nations as a scale to measure disability at an epidemiological level and the two-question pain set has been shown to demonstrate validity in an adult population.⁵⁰ These two questions on pain ("how much pain did you have" and "how bad is the pain") have been adapted for use with children and are included in the study as markers of pain persistence and distress.

The RN Consultation has a two-fold objective: 1) To gather clinical information to assist the study team in assessing and treating the child's PIUO and 2) to provide the parent with a consultation in regards to any measurements they might take or have taken to relieve their child's PIUO. The clinical information relevant in this regard includes any changes in health, medications or interventions outside the study (including care provided by community physicians, therapists, and alternative medicine practitioners) that might impact PIUO.

Once on the PIUO Pathway (regardless of starting arm) children will receive the intervention for a minimum of 10 weeks. Children will stay on the Pathway until the condition improves/resolves or until all investigations and interventions within the PIUO Pathway have been exhausted without improvement or resolution to the condition or after 6 months have passed, whichever comes first. There will be a follow-up assessment 2 months after the child completes the PIUO Pathway either with or without resolution or improvement.

Efficiency of the PIUO Pathway will be measured by tracking time needed, and number of investigations required, for those patients who turn out to have an identifiable cause for pain and irritability. Parents will be given a chance to provide feedback on the study and their participation via a survey, answering questions detailed in the Family Feedback Form (Appendix 11)

STUDY PROCEDURES

The PIUO Pathway

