The PIUO Pathway focuses on eliminating undiagnosed, but treatable sources of PIUO. It targets PIUO in an intentional, focused, timely sequential order of standardized steps with physician and dedicated nurse support. The PIUO Pathway is implemented by clinicians (MD and RN) with expertise in treating pain in children. A key element is the ongoing and frequent contact between families and clinicians to coordinate tests and treatments along the PIUO Pathway and to monitor results or adverse events (see Data Monitoring Plan for handling and reporting of adverse events).

As shown in Appendix 1b, the PIUO Pathway has 2 steps (described in detail below). Each participant proceeds through the PIUO Pathway as long as their pain persists, but may not go through all steps of the PIUO Pathway in case their pain is resolved at any stage.

- Step 1 is a thorough history and patient evaluation, including directed testing.
- Step 2 is a series of screening tests to further explore any potential underlying disease or injury not apparent based on history and physical examination.

Step 1 begins with a detailed History and Physical Examination (Hx&PE). This includes a pain history to identify known and unknown sources of past and current pain, and a recording of previous assessments and treatments directed towards pain.⁵¹ The history will include a record of medications, surgical interventions, physical and behavioural interventions from allopathic and alternative/complementary approaches. If families have any detailed observations demonstrating their child's PIUO episodes (e.g. diary or video); these will be reviewed by the study clinician. Clinician assessment of those observations will be considered clinical data, but the media will not become part of the dataset. The MD Assessment to be undertaken in Step 1 is outlined in full in Appendix 6. Appendix 6b constitutes a summary of the assessment to be filled out by the SRN. While the MD Assessment will be used as clinical data to assess and treat the participants' pain and irritability, the Summary Sheet will contain research data to be entered into REDCap. The data to be collected regards whether the MD Assessment was carried out thoroughly by the MD, rather than the results of the assessment.

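### Pathway efficiency is measured only in children in whom a cause is found, so it describes effort to diagnosis among the diagnosed, not efficiency for a child who enters

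*Protocol*

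**What the plan says.** The Protocol's Study Sequence section defines the efficiency measure in one sentence: "tracking time needed, and number of investigations required, for those patients who turn out to have an identifiable cause for pain and irritability". The Objectives section lists identification of common causes as a secondary outcome, so the restriction is by a result of the Pathway itself.

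The exit rules are in the same section. Once on the Pathway, "children will receive the intervention for a minimum of 10 weeks". Failing improvement or resolution, a child stays "until all investigations and interventions within the PIUO Pathway have been exhausted without improvement or resolution to the condition or after 6 months have passed"; the earliest of these events ends the child's time on the Pathway. The description of the PIUO Pathway under Study Procedures adds that a child "may not go through all steps of the PIUO Pathway in case their pain is resolved at any stage". It also sends a child whose Step 1 is unrevealing on to Step 2, which consists of four standard screening tests.

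Neither the Objectives nor the Analysis section gives an efficiency measure over all children who start the Pathway.

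**The concern.** Whether a child counts towards the efficiency figure is known only after the Pathway has been applied. All time and tests spent on children with no cause found drop out of the figure. The measure also behaves perversely: if a late, test-heavy diagnosis is missed, that child leaves the group and the reported efficiency improves.

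This matters because of how the result is meant to be used. The Study Design section describes this kind of work as demanding in time and resources and presents clinical pathways as a way to avoid inefficiency. The Justification section expects the results to become a practice guideline. A clinic that adopts the Pathway cannot know at Step 1 which children will turn out to have a cause. It needs to know what the Pathway takes per child entered and per cause found, and the planned figure gives neither.

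**Working it through.** The Protocol states no efficiency figure, so there is none to reproduce. Its only design calculation, 57 per group for the primary comparison, does not bear on this point.

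**Notation**

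- p: share of children in whom a cause is identified. Not given in the Protocol.
- T1: mean Pathway time in those children. Not given.
- T0: mean Pathway time in the others. Not given.

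**Three quantities**

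- Planned figure: T1.
- Mean per child entered: p × T1 + (1 − p) × T0.
- Time per cause found: [p × T1 + (1 − p) × T0] / p = T1 + T0 × (1 − p)/p.

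The third exceeds T1 for any p below 1 and any T0 above 0, so understatement per cause found follows from the algebra. The second exceeds T1 only if T0 exceeds T1, which is an empirical matter. The same holds for counts of investigations.

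**Illustrative inputs, all proxies**

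- p = 0.63 and T1 = 13 weeks, from the pilot results in the Justification section. This lets resolution stand in for cause found, time to resolution stand in for time to a cause, and a median stand in for a mean. The pilot had 10 children.
- T0 between 10 weeks (the stated minimum on the Pathway) and 26 weeks (the 6-month limit).

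**Results at p = 0.63**

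- T0 = 26: 0.63 × 13 + 0.37 × 26 = 8.19 + 9.62 = 17.8 weeks per child; 17.81 / 0.63 = 28.3 weeks per cause found.
- T0 = 13: 8.19 + 4.81 = 13.0 weeks per child; 13.0 / 0.63 = 20.6 per cause found.
- T0 = 10: 8.19 + 3.70 = 11.9 weeks per child; 11.89 / 0.63 = 18.9 per cause found.

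Break-even for the per-child mean: if a share f of the children without a cause leave at 10 weeks and the rest stay 26, T0 = 10f + 26(1 − f). Setting this equal to 13 gives f = 13/16 = 81%. Below that share, the planned figure is lower than the per-child mean.

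**Varying p as well** (T1 = 13; weeks per child entered / weeks per cause found)

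| p | T0 = 10 | T0 = 26 |
|---|---|---|
| 25% | 10.8 / 43.0 | 22.8 / 91.0 |
| 50% | 11.5 / 23.0 | 19.5 / 39.0 |
| 63% | 11.9 / 18.9 | 17.8 / 28.3 |
| 80% | 12.4 / 15.5 | 15.6 / 19.5 |

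The per-child mean falls on either side of 13. The per-cause figure is above 13 in every cell.

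**Step 2 screening tests.** Assume p = 0.63, half of the causes found at Step 1 with no screening tests, and all four tests in every other child. The restricted group then averages 0.5 × 4 = 2.0 tests. The mean per child entered is 0.63 × 2.0 + 0.37 × 4 = 2.7, and tests per cause found are 2.74 / 0.63 = 4.3. This ignores directed tests at Step 1 and the rule that recent screens are generally not repeated.

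**The case against.** The strongest reply is that the stated quantity is coherent. Time needed and investigations required can be read as what it takes to reach a cause, which has no endpoint where none is found. Effort to diagnosis among diagnosed children is a legitimate description, and the Protocol does not claim that it represents every child entered. This stands as a reason to keep the figure, but not as a reason to call it the efficiency of the Pathway.

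A second reply is that efficiency is a single descriptive measure outside the listed primary and secondary outcomes, and that such detail belongs in a statistical analysis plan. The low stakes are conceded. But the Protocol does not leave the population open; it fixes it.

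A third is that identification of causes is a secondary outcome, so readers may see the yield next to the restricted figure. That would help them see how many children it covers. Yet p and T1 without T0 do not give the time per child or per cause found.

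A reader might also infer that children without a cause necessarily use the most time and tests because they stay to the end. The documents do not support this. Exit turns on improvement, exhaustion or 6 months, so a child can improve and leave with no cause found, and a child with a cause can stay on for treatment. Exhaustion may come before 6 months. A suggestive Step 1 can itself generate directed tests. Longer stays and more tests in the children left out are plausible, not established.

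**Conclusion.** The point holds in a limited form. The planned measure is conditional on a result of the Pathway and does not describe efficiency for a child who enters. Understatement per cause found is certain whenever children without a cause use any resources. Understatement of the mean per child entered is the expected direction but not certain.

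The size cannot be computed from the Protocol, because the share with a cause and the time and tests by group are not given. Under the pilot proxies the range against 13 weeks is 11.9 to 17.8 per child entered and about 19 to 28 per cause found. It would be tempting to present 17.8 and 28 weeks as the estimate. They are the upper ends, and they require every child without a cause to remain for the full 26 weeks.

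It would also be wrong to read the restriction as conditioning on treatment success. Success in this trial is a low Pain Survey category on consecutive visits, which is not the same as a cause being found. The primary comparison and its sample size are not affected, so this is a worthwhile improvement and not a threat to the trial's main result.

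**What to change.** Reword the efficiency sentence in the Study Sequence section so that time and number of investigations are measured in every child who starts Step 1, from either arm, with the clock starting at Step 1. Then report:

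- time and investigations per child entered;
- total time and total investigations divided by the number of causes found;
- the cumulative incidence of an identified cause by weeks since Step 1, up to Pathway exit or 6 months, with children who leave without a cause kept in the denominator;
- the figures restricted to children with an identified cause, labelled as a description of that group.

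The cost is a little more analysis and possibly a less favourable figure. Who will have a cause is unknown at Step 1, so prospective tracking has to cover every child anyway. If sites had meant to extract these data afterwards for identified cases only, there would be some added data collection.

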Our goal is to improve PIUO beyond what has been undertaken by the child's usual clinical teams. The primary outcome is improved pain control for non-verbal children with SNI as shown in a reduction of their pain and irritability scores for the pathway group compared to the control arm for two consecutive weeks starting at week 8 or 10. Secondary outcomes include successful identification of common causes of pain and irritability in non-verbal children; decreased pain severity between baseline and the end of pathway (within 8 months post-baseline); improved family quality of life; ease of implementation of the PIUO Pathway for clinicians. We will also collect family feedback on the implementation of the PIUO Pathway.

Justification

PIUO is a source of stress for children and families. Research undertaken by our team and by others over the last fifteen years has described the manifestations of pain and irritability in children with SNI, developed assessment tools, explored its causes, and recorded the impact on families.^{5,14,18-20} With this study, we are moving forward to intervention. Many of the team members in this study are clinicians with leadership roles in programs providing care to children with SNI. Therefore findings from this study, in the form of clinical guidelines, may be rapidly translated into practice.

We have verified the importance of this research through years of focus on this issue. We developed the PIUO Pathway based on best evidence from the literature and expert opinion and performed a pilot observational study in 10 non-verbal children with SNI. The children ranged in age from 5 to 17 years and their SNI had a wide variety of causes, with high degrees of medical complexity and communication impairment. The children were recruited from community pediatric practices and all were followed by hospital sub-specialists. Our results were surprising: while it might be assumed that evaluation for pain and irritability would be thorough and revealing, just the opposite occurred in these children.³⁶ We found that:

- No child in the pilot study had been fully evaluated for PIUO before enrolling. PIUO assessment was conducted in a disorganized, scatter-shot manner, with each child receiving only partial elements of a comprehensive evaluation.

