In Step 1, any information gained may then lead to directed testing with imaging or laboratory studies. As an example of directed testing, if the child has pain with transfers into a wheelchair the physician may order an x-ray to rule out hip dislocation. Any findings from directed testing (or screening testing as described below) will be shared with the child's usual care team (i.e. primary team) via the standard reporting system available at each study site (paper and/or electronic record). Findings related to pain sources will be managed by the Site Lead clinician, whereas incidental findings will be referred for management by the child's usual care team.

If Step 1 is unrevealing, **Step 2** consists of a series of screening tests. The screening tests are designed to look for sources of pain that would not necessarily be revealed in a careful Hx&PE or directed testing. If any screening test has already been completed within 6 months prior to the participant enrolling in the PIUO Pathway, it is not repeated, unless the pain and irritability symptoms have changed since the test was done. The exception is the Hx&PE, which is always done at the Step 1 visit by the study team. The utility of the step approach is provided by a study that used directed tests and screening to assess PIUO in a limited and more expensive workup with nuclear medicine imaging.⁵²

The 4 PIUO standard screening tests are:

1. Urinalysis
2. Ultrasound - abdominal
3. Gastric pH (if G-tube present)
4. Bloodwork , including:
 - i. Complete Blood Count/CBC - White blood cells/WBC, Hemoglobin/Hgb, Hematocrit/Hct
 - ii. Alkaline Phosphatase/Alk Phos
 - iii. Alanine Aminotransferase/ALT

- iv. Aspartate Aminotransferase/AST
- v. Bilirubin
- vi. C reactive protein/CRP
- vii. Creatinine/Cr
- viii. Electrolytes – Sodium/Na, Potassium/K, Calcium/Ca, Magnesium/Mg, Chloride/Cl and Phosphorus/PO4
- ix. Ferritin
- x. Gamma Glutamyl Transpeptidase/GGT
- xi. Immunoglobulin A/IgA
- xii. Lipase
- xiii. Anti-endomysial antibodies/TTG

Although the above screens are standard of care, the order of these tests (e.g. performing Hx & PE) then Step 1 tests, and then moving to Step 2 screens is a novel approach being tested here. If Step 2 imaging or exams were required as part of Step 1, then they will not be repeated at Step 2.

DATA COLLECTION TOOLS

All Instruments to be used for data collection will be available in English and French or an interpreter will be available when the tool is used:

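### The protocol keeps the findings of the Step 1 physician assessment out of the research data, but a secondary outcome and the efficiency measure both need a recorded cause for each child

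*Protocol*

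**What the plan says.** Step 1 of the Pathway is a history and physical examination by the study physician, with directed tests where these are indicated. The protocol (Study Procedures, The PIUO Pathway) gives the record of that assessment two roles. First, "the MD Assessment will be used as clinical data to assess and treat the participants' pain and irritability". Second, a summary (Appendix 6b), completed by the study nurse, is the research form: "the Summary Sheet will contain research data to be entered into REDCap". The content of that research data is then limited: "The data to be collected regards whether the MD Assessment was carried out thoroughly by the MD, rather than the results of the assessment".

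Two other places rely on knowing what was found. Study Aims, Objectives: "Secondary outcomes include successful identification of common causes of pain and irritability in non-verbal children". The Study Sequence describes the efficiency measure as follows: "tracking time needed, and number of investigations required, for those patients who turn out to have an identifiable cause for pain and irritability".

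On tests, the Pathway section names the usual care team as the recipient: "Any findings from directed testing (or screening testing as described below) will be shared with" that team. It adds that the Site Lead manages findings that bear on pain. It does not say whether either kind of finding is entered as research data.

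**The concern.** The history and examination are the first point at which a cause can come to light, and their outcome helps decide whether the Step 2 screens are done at all. A sentence that removes their results from the research data therefore works against the outcome that counts causes, and against a measure whose denominator is the children in whom a cause was found.

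At stake is whether the trial can report which causes were found, in how many children and at which step, from data collected prospectively and coded in the same way at four sites. This is more than a detail that a statistical analysis plan could supply later. Such a plan can define how a variable is analysed, but it cannot restore a field that was never collected.

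**Working it through.** The document gives no figure on this point, so there is no calculation to reproduce. The check is to list what the two measures need and then look for where the protocol text says it is captured.

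**What is needed.**
- Cause-identification outcome (Objectives): for each child on the Pathway, whether a cause was identified and which one.
- Efficiency measure (Study Sequence): the same yes/no status, to define the denominator, and a date of identification if the time needed is to run up to the finding. It also needs a count of investigations.

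**Where it could be captured.**
1. *Appendix 6b summary sheet.* Described as research data, but limited to whether the assessment was thorough. Results are expressly left out.
2. *The full physician assessment (Appendix 6).* Classed as clinical data.
3. *Listed instruments (Data Collection Tools).* These are GMFCS, CFCS, FLACC, NCCPC-R, Pain Survey and PROMIS-57. They measure function, communication, pain behaviour, pain level and parental well-being. None records a cause.
4. *Baseline record review and Health Information Form (Study Sequence).* The review covers work-up done before the Pathway. The form is given at the baseline interview, before Step 1.
5. *Biweekly nurse consultation (Study Sequence).* Its purpose is to gather clinical information. The content named is "any changes in health, medications or interventions outside the study". That list is illustrative, so a cause field on the form is possible, but none is described.
6. *Directed and screening tests (The PIUO Pathway).* Findings go to the usual care team. Entry as research data is neither stated nor excluded.
7. *Count of investigations (Study Sequence).* This gives the number of tests. It cannot show a cause recognized by history or examination without a test.

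**Result by route of discovery.**

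| How the cause is found | Position in the protocol text |
|---|---|
| History or examination alone | Results excluded from the only research form described for this assessment |
| Directed test (Step 1) | Not excluded, not stated to be research data |
| Screening test (Step 2) | Not excluded, not stated to be research data |

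**Size.** All 120 children to be randomized (Study Design) could have the Step 1 assessment, because waitlist children cross over to Step 1 after ten weeks. That is a ceiling on the number assessed, not an estimate of the number affected. The children directly exposed are those whose cause is established by history or examination with no confirming test. The pilot summary (Justification) reports that pain resolved in 63% of children, but does not say how many causes were found or by which route, so it cannot supply the missing share.

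**The case against.** The strongest reply is that the restrictive sentence governs one form. Elsewhere the protocol commits to tracking time and investigations in children with a cause, so it evidently intends to know who they are. The Data Storage section keeps Site Lead and nurse notes at the sites and says in general terms that source-document data go into REDCap. The appendix forms and the events grid are not at hand, so a cause field may exist on one of them.

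Much of this stands. A reader might infer that the cause-identification outcome is impossible to derive. The document does not support that: test findings are not excluded, and a cause seen on examination stays in the clinical record and could be abstracted. What does not stand is the suggestion that the general storage statement settles the matter. The sentence on the physician assessment is specific and excludes the results. Retention at site is not collection, and later abstraction would be unplanned and uncoded. The commitment to an efficiency measure shows that the variable is intended; it does not show where it is held.

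A reader might also infer that adverse events could not be related to what the Pathway did. The restrictive sentence says nothing about events or treatments, and the Pathway section refers their handling and reporting to a separate Data Monitoring Plan that is not shown. No conclusion about harms can be drawn.

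Finally, one might size the loss by assuming what share of all causes Step 1 yields. That would count directed-test findings as lost, although Step 1 includes them and the exclusion does not reach them.

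**Conclusion.** The point holds as an internal inconsistency. The protocol excludes the results of the Step 1 physician assessment from the research data, while one secondary outcome and the efficiency measure require a recorded cause per child, and the protocol text names no instrument that captures one. Causes found by history or examination alone are the exposed group; their number cannot be estimated from the document.

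The conclusion rests on the protocol text alone, without the appendix forms. If one of those forms already holds a coded cause, the defect shrinks to a missing cross-reference.

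The consequence is limited. Randomization, the Pain Survey and PROMIS-57 outcomes, their analyses and the sample size do not depend on this. A reader might think the intended practice guideline falls with it, but the Justification section rests the guideline on whether the Pathway helps, which the pain outcome mainly addresses. Cause counts would add to it. This should be fixed, and preferably before or early in data collection, because the gap is hard to repair in a uniform way afterwards.

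**What to change.** Reconcile the sentence on the physician assessment with the Objectives and the Study Sequence. Change it so that Appendix 6b, or another form named in its place, also records:
- cause identified, yes or no, with a coded category;
- date of identification;
- step and source: history or examination, directed test, or screening test.

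State that these fields supply the cause-identification outcome and define the denominator, and where relevant the timing, for the efficiency measure. If an existing form already carries them, name that form and field and correct the restrictive sentence.

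The cost is a few coded fields on a sheet that the study nurse already completes, a small amount of extra data entry, and possibly an ethics notification if the consent wording limits assessment results to clinical use. Clinical care does not change.
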